**Table 2. Primary Estimands**

Primary Estimand for Primary Analysis					
Population	Treatment	Outcome	Summary Measure	Potential intercurrent events	Strategy for intercurrent event
ITT	Initially randomised treatment (Intervention v. Control) and any subsequent changes to treatment over treatment period	Whole fetal brain volume in cm  at 36–38 weeks of gestational age (continuous)	Minimally adjusted mean difference (95%CI) between treatment arms in whole brain volume in cm  , adjusted for gestational age at assessment and the randomization stratification factors (maternal education and municipality economic status)	
 
1. Treatment discontinuation without study withdrawal
 
2. Early study withdrawal
 
3. Treatment non-compliance (intermittent or partial treatment adherence not resulting in treatment discontinuation)
 
4. Dose adjustment
 
	Treatment Policy for all intercurrent events - all observed values will be used, regardless of whether or not the subject had experienced the intercurrent event
		Bayley-III Cognitive score at 4–6 months: Z-score converted raw score of Bayley-III cognitive subscale (continuous)	Minimally adjusted mean difference (95%CI) between treatment arms in Bayley-III cognitive score, adjusted for child age at assessment and the randomization stratification factors (maternal education and municipality economic status)		
		Bayley-III Cognitive composite score at 4–6 months: Score based on conversion of Bayley-III cognitive scaled score (continuous)	Minimally adjusted mean difference (95%CI) between treatment arms in Bayley-III cognitive composite score, adjusted for child age at assessment and the randomization stratification factors (maternal education and municipality economic status)		
		BERA absolute latencies at 4–6 months for wave I in ms (continuous)	Minimally adjusted mean difference (95%CI) between treatment arms in absolute latencies for wave I, adjusted for child age at assessment and the randomization stratification factors (maternal education and municipality economic status)		
		BERA absolute latencies at 4–6 months for wave III in ms (continuous)	Minimally adjusted mean difference (95%CI) between treatment arms in absolute latencies for wave III, adjusted for child age at assessment and the randomization stratification factors (maternal education and municipality economic status)		
		BERA absolute latencies at 4–6 months for wave V in ms (continuous)	Minimally adjusted mean difference (95%CI) between treatment arms in absolute latencies for wave V, adjusted for child age at assessment and the randomization stratification factors (maternal education and municipality economic status)		
		BERA interpeak latencies at 4–6 months for wave I–III interval in ms (continuous)	Minimally adjusted mean difference (95%CI) between treatment arms in interpeak latencies for wave I–III, adjusted for child age at assessment and the randomization stratification factors (maternal education and municipality economic status)		
		BERA interpeak latencies at 4–6 months for wave III–V interval in ms (continuous)	Minimally adjusted mean difference (95%CI) between treatment arms in interpeak latencies for wave III–V, adjusted for child age at assessment and the randomization stratification factors (maternal education and municipality economic status)		
		BERA interpeak latencies at 4–6 months for wave I–V interval (central conduction time) in ms (continuous)	Minimally adjusted mean difference (95%CI) between treatment arms in interpeak latencies for wave I–V, adjusted for child age at assessment and the randomization stratification factors (maternal education and municipality economic status)		

	IOWA mean latency at 6 months	Minimally adjusted mean difference (95%CI) between treatment arms in IOWA mean latency, adjusted for child age at assessment and the randomization stratification factors (maternal education and municipality economic status)
	IOWA task error at 6 months	Minimally adjusted mean difference (95%CI) between treatment arms in IOWA task error, adjusted for child age at assessment and the randomization stratification factors (maternal education and municipality economic status)
	VPC novelty preference score at 6 months	Minimally adjusted mean difference (95%CI) between treatment arms in VPC novelty preference score, adjusted for child age at assessment and the randomization stratification factors (maternal education and municipality economic status)
	VPC mean familiarization fixation at months	Minimally adjusted mean difference (95%CI) between treatment arms in VPC mean familiarization fixation, adjusted for child age at assessment and the randomization stratification factors (maternal education and municipality economic status)

## 5.2. Sensitivity Analyses

In all primary analyses for the primary outcomes, inverse probability of censoring weights (IPCW) will be estimated to address potential bias from outcome attrition. The missingness model will be fit using logistic regression with a prespecified set of covariates, including allocation group, randomization stratification factors (maternal education and municipality economic status), baseline characteristics listed in **Table 1**, and other primary outcomes measured prior to the outcome visit (e.g., fetal whole brain volume when modeling the cognitive score) that are plausible predictors of both censoring and the outcome. Stabilized weights will be computed conditional on allocation group and the randomization stratification factors, and weights will be truncated at the 1st and 99th percentiles (0.5th and 99.5th in sensitivity analyses). Diagnostics will include summaries of the weight distribution, effective sample size, and covariate balance before and after weighting. Robustness to model misspecification will be assessed using augmented IPCW estimators.

We will not perform a per-protocol analysis given the high compliance with both the probiotics/placebo and omega-3 FAs interventions.

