## 2.6. Sample Size

Sample size calculations were based on the hypothesized effect size of 0.40 standard deviation (SD) between intervention and control groups on fetal whole brain volume at 36–38 weeks of

gestational age, and on Bayley-III cognitive scores, BERA indicators, and eye-tracking assessment indicators at 4–6 months of age ( $\alpha=0.05$  and  $1-\beta=0.80$ ). The original protocol assumed an effect size of 0.30 SD and a 20% attrition rate, resulting in a minimum sample size of 400 participants. However, due to recruitment challenges and increased loss to follow-up during the COVID-19 pandemic, which raised the anticipated attrition rate to 33.3% and constrained available funding, a protocol amendment was made. The target sample size was revised to detect a difference of 0.40 SD between groups, generally considered moderate and likely to be of clinical importance, resulting in a lowered estimated minimum sample size from 400 to 300 participants. Effect sizes between 0.30 and 0.40 SD were chosen based on prior findings: for Bayley-III domains, Cohen's  $d$  values in developmental cohorts and preterm interventions fall within this range; neuroimaging studies show between-group brain volume differences of approximately 0.30–0.50 SD in fetuses and neonates; and intervention-related physiologic/eye-tracking changes are typically described in similar effect size terms.

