### **3.9. Handling of Missing Data**

We will handle missing data first by tabulating the proportion of subjects lost to follow-up by allocation groups and examining if missingness differs significantly (e.g., >10% absolute difference) by allocation groups or key baseline characteristics. Additionally, baseline characteristics of participants with available outcome data will be compared to those with missing outcome data. To further assess potential bias introduced by missingness, we will evaluate balance in baseline covariates between allocation groups, both in the original trial sample and the sample retained at follow-up. Efficacy analyses and other exploratory analyses will be performed in the full analysis set (i.e., all subjects randomly assigned to the study, including those who did not receive a dose of study treatment).

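### The IPCW missingness model in SAP 5.2 has no arm-specific terms, so as written its weights do not correct loss whose predictors act differently in the two arms

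*SAP*

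**What the plan says.** Section 3.5 makes the analysis complete-case, and Section 5.1 adjusts the primary model only for age at assessment and the two stratification factors. Section 5.2 (primary outcomes) then plans that "inverse probability of censoring weights (IPCW) will be estimated to address potential bias from outcome attrition". The missingness model is described once: "The missingness model will be fit using logistic regression with a prespecified set of covariates, including allocation group, randomization stratification factors", followed by the baseline variables of Table 1 and earlier primary outcomes. On the weights it adds: "Stabilized weights will be computed conditional on allocation group and the randomization stratification factors, and weights will be truncated".

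Section 5.2 contains two further safeguards: "Diagnostics will include summaries of the weight distribution, effective sample size, and covariate balance before and after weighting", and "Robustness to model misspecification will be assessed using augmented IPCW estimators". It does not give the outcome model of the augmented estimator.

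Section 3.9 plans two checks. One is "examining if missingness differs significantly (e.g., >10% absolute difference) by allocation groups or key baseline characteristics". The other is that "we will evaluate balance in baseline covariates between allocation groups, both in the original trial sample and the sample retained at follow-up". Section 5.1.2 adds baseline covariates associated with the outcome at p < 0.1 in a secondary, baseline-adjusted model.

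The SAP nowhere mentions an interaction between allocation and a covariate in the missingness model. Where it does intend an interaction with allocation, for effect modification in Section 5.3, it says so.

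**The concern.** A logistic model with allocation as one covariate among others gives every other predictor the same slope in both arms. Stabilising on arm and strata changes only the numerator of the weight; the covariate slopes in the denominator stay common.

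Loss can distort a randomised comparison through an observed covariate in two ways. The arms may lose different proportions, or the covariate may act differently on loss in each arm. The allocation main effect deals with the first. In the second case, which can produce the larger bias, a common slope averages two mechanisms and shifts both arms by about the same amount, so the difference between them stays where it was.

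Section 2.6 reports that pandemic conditions "which raised the anticipated attrition rate to 33.3" per cent, and IPCW is the named attrition analysis for all 13 primary estimands in Table 2. If it agrees with the complete-case result because it cannot see this mechanism, that agreement is not evidence of robustness.

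**Working it through.** **Inputs from the SAP.** 157 per arm (2.4); 33.3% anticipated attrition, design effect 0.40 SD, power 0.80 (2.6); two-sided 0.05 and a primary model adjusted for age and strata only (5.1); weights stabilised and truncated at the 1st and 99th percentiles (5.2).

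**Assumed, because the SAP gives no values.** One standardised baseline covariate X; its correlation ρ with the outcome (0.3 to 0.5); log-odds slopes b₁ and b₀ of retention on X in the two arms; equal loss in both arms unless stated; true effect 0.

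**The plan's own figure.** n per arm = 2(1.96 + 0.842)² / 0.40² = 98.1, so 99 per arm and 198 in total; 198 / (1 − 0.333) = 297. The stated 300 reproduces and is not in dispute.

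**Approximation by hand.** With retention r, a small slope b gives P(retained | X) ≈ r + r(1 − r)bX. The mean of X among those retained therefore shifts by about b(1 − r), and

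complete-case bias ≈ ρ × (b₁ − b₀) × (1 − r).

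- ρ = 0.3, gap 0.2: 0.3 × 0.2 × 0.333 = 0.020 SD
- ρ = 0.4, gap 0.5: 0.4 × 0.5 × 0.333 = 0.067 SD
- ρ = 0.4, gap 1.0: 0.4 × 1.0 × 0.333 = 0.133 SD
- ρ = 0.5, gap 1.0: 0.5 × 1.0 × 0.333 = 0.167 SD

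Weights from a common slope b̄ take off about b̄(1 − r) in each arm. That cancels in the difference, so the bias remains.

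**Simulation (bias in SD).** The first three rows use 2,000 replicates at N = 314. The two ρ = 0.4 rows with a slope gap come from one set of runs and the ρ = 0.5 row from another. The last row is one run of 1,000,000. The sign follows which arm is given which slope.

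| Scenario | Complete case | IPCW as written | IPCW arm-specific |
|---|---|---|---|
| ρ 0.5, slopes −0.5 / +0.5 | −0.156 | −0.156 | −0.007 |
| ρ 0.4, slopes +0.5 / −0.5 | 0.125 | 0.125 | 0.004 |
| ρ 0.4, slopes +0.5 / 0 | 0.063 | 0.065 | 0.005 |
| ρ 0.4, common slope 0.5, retention 60% / 73.4% | 0.026 | 0.004 | 0.004 |

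The last row shows that a difference in loss rate alone is removed by the model as written.

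**Precision.** At N = 314 the empirical SD of the estimate in the two ρ = 0.4 rows with a slope gap was 0.141 with the weights as written and 0.139 with arm-specific weights. With 18 covariates in the model the bias was 0.133 SD for both complete case and IPCW as written. Across the 1- and 18-covariate runs, arm-specific weights left 0.003 to 0.017 SD, with an SD of about 0.14 either way.

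**Effect on error rate.** With bias 0.125 and SD 0.141 the shift is 0.125 / 0.141 = 0.89 standard errors. A nominal 5% test of a true null then rejects with probability Φ(−1.07) + Φ(−2.85) ≈ 0.142 + 0.002, about 14%.

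**The case against.** A reader might infer that the attrition analysis as a whole can neither detect nor remove arm-specific loss. The SAP does not support that, for five reasons.

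- **Detection.** The Section 3.9 comparison of baseline balance in the retained sample would show the pattern. With slopes of ±0.5, the mean between-arm imbalance in X was 0.32 SD, and it exceeded 0.1 SD in 96% of simulated trials. The weighted balance diagnostic in 5.2 would show the same 0.32 SD still present after weighting, if it is tabulated between arms.
- **Augmented IPCW.** With the same common-slope weights and a correct outcome model by arm, the bias fell to 0.002 SD or less in absolute value. With a misspecified outcome model (omitted quadratic term, slopes 0.8 and −0.2) it was −0.025, against 0.113 for plain IPCW as written and 0.007 with arm-specific weights.
- **Baseline-adjusted model.** Section 5.1.2 would select a covariate this prognostic in at least 99% of simulated trials. With ρ = 0.5 and slopes of ±0.5 it took the bias from −0.163 to −0.002.
- **Silence is not exclusion.** The SAP lists covariates and does not forbid interactions. Equal slopes are the natural reading, not an explicit statement.
- **Plausibility.** The capsules look identical and the rise in attrition is attributed to the pandemic, so opposite slopes are not the expected case. A bias of 0.15 SD would be 0.15 / 0.40 = 38% of the design effect, but nothing in the SAP makes that the likely size.

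All five stand, and they limit the point without removing it. No balance result is tied to a change in the weights. The protection from the augmented estimator depends on an outcome model that is not named. The adjusted model is a secondary analysis with data-driven selection and is not the attrition safeguard. A sensitivity analysis should be able to test an assumption such as equal slopes, not build it in.

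**Conclusion.** The concern holds for the weights, not for the whole of the attrition work. As written, the IPCW estimate corrects a difference in loss rates but leaves the complete-case bias essentially unchanged when baseline predictors of loss act differently in the two arms. With 33.3% loss, correlations of 0.3 to 0.5 and slope gaps of 0.2 to 1.0 log-odds per SD, that bias runs from about 0.02 to 0.16 SD, or 5% to 40% of the 0.40 SD design effect (0.02 / 0.40 and 0.16 / 0.40). The lower end is negligible. The upper end needs opposite slopes in the two arms, which is an assumption. Arm-specific weights reduce the bias to about 0.02 SD or less. The change is a cheap improvement to a sensitivity analysis; the primary analysis itself is not shown to be invalid.

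**What to change.** In Section 5.2 (primary outcomes):

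1. Fit the missingness model separately in each arm, or add a short prespecified list of allocation-by-covariate interactions. Penalise the fit if it is unstable: 157 × 0.333 gives only about 52 losses per arm, or about 3.5 for each of the 15 baseline variables in Table 1.
2. Build the stabilised weights from that model.
3. Name the outcome model of the augmented estimator and fit it by arm.
4. State that covariate balance before and after weighting is reported between arms.

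The cost is a few sentences of SAP text and a few lines of code, with no new data. The downside is more parameters in the missingness model; in the simulations this cost no visible precision.

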## 5.3. Subgroup Analyses

As a secondary objective, we will assess for potential effect modification on the primary outcomes by testing an interaction term between the allocation group and the factors listed below. We will present the differences between the Intervention and Control groups stratified by the effect modifier if the interactions are significant at  $p < 0.1$ .

- **Child sex:** Biological differences, different care practices, or other psychosocial practices may modify the effect of interventions on girls vs boys.
- **Birth order:** Compared to second-born or greater (multiparous mothers), first-born tend to be smaller and may be associated with lower development, thus modifying the effect of interventions.

- **Maternal pre-pregnancy BMI status:** Overweight/obesity may change gut microbiota, including during pregnancy; therefore, it may modify the effect of our intervention between mothers with vs without overweight/obesity using a BMI cutoff of  $\geq 25$  kg/m^2.
- **Baseline maternal anemia:** Anemia during pregnancy has been associated with slower brain development, which may modify the effect of interventions between mothers with vs without anemia.
- **Baseline maternal age:** Biological differences, differential care practices, or differential social support networks due to different maternal age may modify the effect of the interventions on child development. We will first use maternal age as a continuous variable to test interactions. Significant interactions will be further examined with stratified analyses.
- **Baseline maternal education:** Maternal education has been consistently associated with child development and may modify the effect of interventions between mothers with low vs high education. We will use a cutoff of incomplete secondary schooling (<9 years of formal education) to define “low education” and secondary completion or greater as “high education”.
- **Baseline socioeconomic status:** We will categorize subjects based on monthly household expenditure into quintiles, then dichotomize into the highest quintile vs. the lowest four quintiles.
- **HOME Inventory score at 4–6 months:** Children from households with lower nurturing and stimulation of the home environment may have greater potential to benefit from the intervention. We will first use the HOME Inventory score as a continuous variable to test interactions. Significant interactions will be further examined with stratified analyses.

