## 2.2. Secondary Objectives

The hypotheses of secondary objectives are:

- Compared to the control group, fetus of women who receive daily probiotics and higher-dose omega-3 FAs supplements will show higher cerebrum, white matter, deep gray matter, cerebellum, and brainstem volumes at 36–38 weeks of gestational age.
- Compared to the control group, children of women who receive daily probiotics and higher-dose omega-3 FAs supplements will show higher receptive language, expressive language, language composite scores, fine motor, gross motor, and motor composite scores of Bayley-III at the age of 4–6 months.
- Compared to the control group, children of women who receive daily probiotics and higher-dose omega-3 FAs supplements will show higher cue facilitation and lower cue interference assessed by the IOWA task at the age of 4–6 months.
- The intervention effects on each outcome will differ by specific subgroups, including child sex, birth order, maternal pre-pregnancy body mass index (BMI) status, maternal anemia, maternal age, maternal education, socioeconomic status, and home environment.

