### **3.7. Adjustment for Multiplicity**

No adjustment for multiple comparisons will be performed.

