## 5. ANALYSIS OF THE PRIMARY OUTCOME(S)

### 5.1. Main Analysis

We will perform all analyses after the last participant in the follow-up study has completed their visit. We will review the characteristics of the study sample as blinded cohort. First, we will use fake IDs and scrambled group code to write the script for analysis and create dummy tables and figures. Once the script, tables, and figures are ready, we will insert the correct IDs with blinded group code (e.g., A vs. B) and create the draft of the interpretation of the results for each case (e.g., if “A” is the Control group vs. if “A” is the Intervention group). We will finally reveal the group assignments after all authors have reviewed and approved the results for the primary outcomes. Unblinded analyses will be performed for secondary analyses, such as effect modification and subgroup analyses.

For all outcomes, the primary analysis to answer each objective will be a minimally adjusted model controlling only for child age at assessment and the randomization stratification factors (maternal education and municipality economic status). In secondary analyses, we will estimate adjusted parameters by including additional covariates—baseline characteristics, as well as post-enrollment and follow-up variables—in addition to those included in the primary analyses.

Unless otherwise specified, we will use two-sided confidence intervals at the 0.05 significance level for all analyses. For example, we are not powered to conduct subgroup/effect-modification analyses, so these secondary objectives will be exploratory and considered significant at the  $\alpha=0.10$  level. All hypothesis testing in this analysis plan is based on a two-sided superiority framework.

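### Section 5.3 shows stratified effects only if the interaction has p<0.1; over 104 unadjusted tests about 10 would pass by chance if no true interaction exists, and displayed interactions are inflated on average

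*SAP*

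**What the plan says.** Effect modification is a stated secondary objective. Section 2.2 words it as a hypothesis: "The intervention effects on each outcome will differ by specific subgroups", followed by eight factors.

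Section 5.3 (under the primary outcomes) gives the method: "we will assess for potential effect modification on the primary outcomes by testing an interaction term" between allocation and each of those factors. It then sets the display rule: "We will present the differences between the Intervention and Control groups stratified by the effect modifier if the interactions are significant at" p<0.1. Maternal age and HOME score are tested first as continuous variables, and stratified analyses follow only if the interaction passes.

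Section 5.1 sets the threshold and the label together: "we are not powered to conduct subgroup/effect-modification analyses, so these secondary objectives will be exploratory and considered significant at the" 0.10 level. It adds that "All hypothesis testing in this analysis plan is based on a two-sided superiority framework". Section 3.7 states: "No adjustment for multiple comparisons will be performed".

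The subgroup section for secondary outcomes says none will be done, so only the primary outcomes in Table 2 enter the count. The SAP does not say whether interaction estimates that miss p<0.1 will be reported, or that the number of tests will be stated.

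**The concern.** Three features act together. There are many tests, each has little power by the plan's own account, and the result of each test decides whether its stratified effects are shown. With many tests at 0.10, some pass by chance. With low power, an estimate has to be large to pass, so those that pass overstate the true interaction on average. A reader who sees the stratified effects that passed, without those that did not, cannot place them in context.

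The label adds to this. Lack of power is given as the reason for a looser threshold, and results that meet it are then called significant. At stake is how one stated secondary objective is reported. The primary comparisons are not affected.

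**Working it through.** **The plan's own sample size.** Section 2.6 gives 0.40 SD, alpha 0.05, power 0.80, 33.3% attrition and a minimum of 300. Per arm, n = 2 × (1.96 + 0.842)² / 0.40² = 98.1, so 99, or 198 in total. Then 198 / (1 − 0.333) = 297, which agrees with 300. The design basis is sound for the main effect.

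**Number of tests.**
- Outcomes in Table 2: whole brain volume 1, Bayley-III cognitive 2, BERA 6, IOWA 2, VPC 2, which makes 13. The myelination index is not counted because section 2.7.1 drops it.
- Modifiers in section 5.3: child sex, birth order, BMI status, anemia, maternal age, maternal education, socioeconomic status and HOME score, which makes 8.
- 13 × 8 = 104 tests. Of these, 6 × 13 = 78 use a two-level modifier and 2 × 13 = 26 use a continuous one (maternal age, HOME score).

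**Chance passes if no true interaction exists.** 104 × 0.10 = 10.4. Correlation between tests does not change this mean, but it widens the spread. If the tests were independent, the SD would be √(104 × 0.10 × 0.90) = 3.1. They are not: the three BERA interpeak latencies are differences of the three absolute latencies, and both Bayley-III cognitive scores come from one subscale. A simulation with that structure (assumed: 200 completers, correlation 0.9 between the two Bayley-III scores) gave a mean of 10.3, an SD of 3.9 and a 95% range of 4 to 19.

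**Size needed to be shown.** Assumptions: 314 randomised (157 per group, section 2.4) less 33.3% leaves 209 completers; outcome SD 1; two-level modifier with share p in one level; 1:1 allocation within levels. Then

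SE(interaction) = √(4/(Np) + 4/(N(1 − p))), and the display threshold is 1.645 × SE.

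- p = 0.5: SE = √(4/104.5 + 4/104.5) = 0.277; threshold 0.455 SD.
- p = 0.2 (the split that section 5.3 creates for socioeconomic status): SE = √(4/41.8 + 4/167.2) = 0.346; threshold 0.569 SD.

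For other N the threshold scales with 1/√N. With 200 completers it is 0.47 and 0.58 SD. With all 314 analysed it would be 0.37 and 0.46 SD.

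**What the filter does to displayed interactions.** The estimate is taken as normal around the true value and kept only if it exceeds the threshold in absolute size (N = 209):

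| Split | True interaction (SD) | Chance of display | Mean size shown (SD) | Shown / true | Shown estimates above truth |
|---|---|---|---|---|---|
| 50/50 | 0.2 | 19% | 0.60 | 3.0 | all |
| 50/50 | 0.4 | 42% | 0.66 | 1.6 | all |
| 50/50 | 0.8 | 89% | 0.86 | 1.07 | 56% |
| 20/80 | 0.2 | 16% | 0.74 | 3.7 | all |
| 20/80 | 0.4 | 31% | 0.79 | 2.0 | all |
| 20/80 | 0.8 | 75% | 0.95 | 1.2 | 67% |

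At a true 0.2 SD, about 5% (50/50) and 8% (20/80) of displayed interactions have the wrong sign. The SAP gives no expected interaction size, so these true values are a range and not a forecast.

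**The case against.** The plan does several things well. The eight modifiers are prespecified and most carry a rationale. It tests interactions and does not compare p-values within subgroups. It leaves the secondary outcomes out, admits the lack of power and calls the work exploratory. A 0.10 screen for low-powered interactions is a legitimate design choice. All of this stands, and it limits the seriousness of the point. It does not remove the filter, because the exploratory label does not change which stratified effects are shown, and the same sentence calls them significant.

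Four stronger readings are tempting, and the documents do not support them.

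- **A reader might infer that every displayed interaction is exaggerated.** That follows only if the true interaction lies below the display threshold. At a true 0.8 SD, 56% to 67% of displayed estimates exceed the truth, so a large part do not.
- **A reader might infer that each displayed subgroup effect exceeds the 0.40 SD for which the trial was sized.** The threshold applies to the interaction, which is a difference between two stratum effects; strata of +0.23 and −0.23 SD already give 0.46 SD. In a simulation with 209 completers, a 50/50 split and no true effects, about 22% of displayed stratum effects exceeded 0.40 SD. At 20/80 the small stratum did so in 84% of displays and the large one in 3%.
- **A reader might infer that the plan withholds the interaction tests that fail.** Section 5.3 conditions only the stratified differences on p<0.1. On the interaction estimates themselves it is silent.
- **A reader might apply the thresholds to all 104 tests.** They hold for two-level modifiers only, so not for the 26 continuous tests. Apart from socioeconomic status, the splits are assumed.

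**Conclusion.** The point holds as a matter of reporting. The SAP writes in a significance filter on stratified effects over 104 unadjusted tests that it describes as underpowered, and then calls those that pass significant. The count of 104 follows directly from Table 2 and section 5.3. The figure of about 10 chance passes is conditional on there being no true interaction, and the number could vary widely around it because the tests are correlated.

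The inflation is an average. It is about threefold or more if the true interaction is 0.2 SD, 1.6-fold to twofold at 0.4 SD, and small at 0.8 SD. These figures rest on 209 completers, outcome SD 1, a two-level modifier and the splits shown; covariates that reduce residual variance would lower the thresholds somewhat. The filter and the count do not depend on these assumptions. The change is worth making because it is cheap and uses models that are already planned.

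**What to change.** In section 5.3 (primary outcomes), replace the p<0.1 display condition. Report the interaction estimate with its 95% CI for all 104 modifier-outcome pairs, whatever the p-value, in one supplementary table or forest plot. Beside each, give the Intervention-Control effect with its 95% CI within each level of the modifier. For maternal age and HOME score, give the effect at values named in the SAP beforehand.

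In section 5.1, keep the description as exploratory, remove the statement that these results are considered significant at 0.10, and state that 104 interaction tests are made without adjustment.

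The cost is SAP wording and a longer supplementary table. No new data and no new model are needed. Section 5.1 places the subgroup analyses after unblinding, so the wording should be settled before then.
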